Caregiver Inclusion Criteria:

- MMSE ≥ 26 (with Mungus age and education correction)*
- Providing care for a friend or relative with AD for a *minimum of eight hours* per week for at least the past six months
- Being over the age of 21 years
- Living with or nearby the patient
- Having a telephone
- Planning to stay in the study geographic area for the duration of the study

* For subjects unable to participate in in-person visits, a telehealth version of the MMSE will be given using the same age and education corrected cutoffs.

Exclusion Criteria for Caregiver and Care Recipient Dyads

Exclusion criteria for the dyads include: 1) Presence of significant sensory or motor deficits (e.g., visual or hearing loss, paralysis) in the patient or caregiver that are judged to preclude completion of the study measures; 2) Patient or caregiver is in active treatment for cancer; 3) Patient or caregiver has a terminal illness with a life expectancy of 6 months or less; 4) Patient is in the late stage of the disease, is bed-bound, or nursing home admission planned within 4 months;

5) Procedures Involved*

The study population will include White non-Hispanic, Black/African American and Hispanic caregivers and their loved ones. We anticipate to screen a maximum of 350 caregiver participants. We expect 240 participants (caregiver and care recipient) to complete the study.

The study will be conducted in English or Spanish. We will recruit and randomly assign participants; following a baseline assessment, 240 participants will be enrolled and randomly assigned to one of two groups: 1) Caregiving Condition or 2) Health Promotion (Nutrition) Condition. The entire study is home-based. The intervention will be delivered over 6 months using computer tablet technology in Spanish or English. Assessments will occur in the beginning of the study, 6 months, and 12 months (after completion of the intervention).

Interested participants (caregivers) can contact us via telephone or email. One of our research associates (RA) will provide more information about the study to potential participants. An approved script including verbal consent obtained from the potential participant in order to ask them questions to determine their eligibility criteria. If the participant is eligible for the study, an appointment will be provided, and one of our interventionists will visit the participant and conduct the baseline assessment at the participants' homes in their preferred language (Spanish or English). This assessment with the caregiver will last between 2 and 3 hours. And

the assessment with the care recipient will be about 1.5 hour. In instances where assessments cannot occur in-person we will use a modified battery to conduct the assessment using a telehealth platform. These virtual visits can be broken up into two or more visits if requested by the participants. We will use paper-based forms and/or REDCap to administer the assessments.

The baseline assessment with the caregiver consists of a series of questionnaires assessing the help provided by the CG to the care recipient (e.g., ADLs/AIDLs), the level of burden, stress, and depression perceived by the CG while providing the care, the amount of social support available to the CG, and the preparedness of the CG to provide continuing care to their loved ones. The assessment with the care recipient consists of measures of depression, executive functioning (Trails A & B), working memory (Letters and Number set, digit span), processing speed (digit symbol), and verbal fluency (category fluency). In instances where the assessment is conducted virtually, certain measures may be excluded (e.g., Trails A & B, Digit Symbol). The assessment with the caregiver and care recipient might not be completed in the same visit. The study protocol allows multiple visits to complete the assessments.

During the baseline home visit, the interventionist will go over the written informed consent with the participants (caregiver and care recipient). For virtual visits, participants will review an electronic consent form; if participants do not have a device to provide e-consent, a copy of the consent form will be mailed to the participant for signature. The assessment will not begin unless the participant has a full understanding of the informed consent form and has signed the form. In the event the care recipient can't comprehend or give consent to the assessment, the interventionist will get the assent from the caregiver. Some assessments (randomly) will be recorded for quality assurance purposes.

Upon the completion of the baseline, participants will be notified by the Project Coordinator or designee about their randomization condition: Caregiving or Health Promotion condition. During first intervention session, all participants will receive a computer tablet equipped with WiFi access. The interventionist will provide a brief tutorial on the usage of the computer tablet before starting the activities of the intervention. It is one computer tablet per dyad.

The **Caregiving condition** will have a component for the caregiver and a component for their loved ones (the care recipient). The care recipient component will have a series of cognitive training tasks. The care recipient will meet with the interventionist on a weekly basis. The interventionist will train the care recipients on how to access these training tasks and complete homework/practice sessions. The caregiver has a total of 12 one-on-one sessions throughout the 6 months of the intervention period. Some of these sessions will be joint sessions with the care recipient. The 12 sessions will cover topics such as depression and emotional well-being; self-care and healthy behaviors; strategies for communication; strategies for mood and stress management; and strategies for management of behavioral /cognitive problems. The first, the third, and the last sessions will be at the participant's home when possible. The other sessions will be conducted via the computer tablet using videoconference program. The caregivers will also be part of 5 support group sessions where the facilitator will review the material covered in the individual sessions. For most of the part, the caregivers don't have sessions with the interventionist while the care recipients are present. Although, there will be sessions that will be conducted with both of them together because of the nature of the topic/conversation.

The **Health Promotion condition** will also have a component for the caregiver and one for the care recipient. The care recipient component will consist of mental stimulation exercises such as computer games. And the caregiver component will consist of nutrition and health promotion topics. They will have access to basic educational information from Alzheimer's Association on tips for dealing with the cognitive loss and available community resources.

Similar to participants of the caregiving condition, the caregivers of the Health Promotion condition will also have 12 one-on-one sessions with the interventionist. The first, the third, and the last sessions will be in-person when possible and the others will be via the computer-tablet using video conference program. The care recipient will have weekly sessions with the interventionist and weekly assignments as well. Caregivers and care recipients of this condition will also have some joint sessions throughout the intervention period of 6 months.

In certain cases, we may be unable to visit in the participant's home. In these cases, we will conduct any sessions, trainings or assessments needed over the telephone and/or secure videoconferencing. Care recipient participants may request to reduce the number of sessions with the interventionist.

We will obtain participant written consent for audio/video recording when we go over the Informed Consent Form during the baseline assessment visit. Since participants can withdraw their consent anytime during the study, we will verbally obtain the consent to audio/video record before the actually recording. Participant's agreement to be recorded will become part of the recording.

We will be administering 2 IRB-approved follow-up assessments one 6-months post session 1, and one 12-months post session 1 (regardless of when the 6-month visit occurs).

Participants can choose to keep the computer tablet at the end of the study – 12 months if they complete participation.

6) Data and Specimen Banking*

The study does not collect specimens.

All the data will be stored and secured using the procedure implemented by the Data Manager of Center on Aging and the Center on Aging and Behavioral Research. The access to records and participants data will be allowed only to the study personnel. The data will not contain any identifying information.

Study data request goes through a web-based check-in and check-out procedure implemented by the Center on Aging and the Center on Aging and Behavioral Research. The Data Manager of the Center or designee monitors the logs. Upon granting of the approval, the requester will either get the hard copy of the data or link to access the electronic data. All the data will not contain any identifying information.

7) Data Management*

Preliminary Analyses

Prior to any statistical tests, descriptive statistics, *including* histograms, box plots or scatter diagrams, will be used to assess distribution of variables and their inter-relationships, as well as to detect missing data and outliers for outliers that are deemed to be legitimate values, two types of analyses will be performed and the results compared and reported: the first analysis will include the outliers, and the second will exclude them. Transformations, such as logarithmic or square root transformations will be used for variables with skewed distributions, prior to their inclusion in any analyses that require normality or approximate normality. If normality cannot be achieved through transformations, then non-parametric techniques will be used. Bivariate analyses (e.g., chi-square tests, t tests) will be used to assess patterns of association of factors potentially associated with outcome measures. Appropriate correlational analyses will be performed for each of the independent variables as well as with the outcome variables to identify factors related to outcomes or that are likely to be confounders. Factors that will be considered as potential confounders are those observed to have moderate associations (using a liberal size for preliminary tests of association such as $\alpha=0.25$) with appointment adherence as well as with independent variables specified in the hypotheses. These variables will be controlled for in analyses for specific hypotheses, as appropriate.

Primary Analytic Strategy

Our plan for the main analyses is to use the General Mixed Model (Ware, 1985), which is an analytic strategy that can be employed for the hypotheses under each specific aim. This model is suitable for analysis of unbalanced data, does not require the assumption of normality of the dependent variable (in fact it can be used when the response of interest is a binary variable or a count variable), can incorporate account for missing data in statistical models and is implemented in different analytical software packages such as the Proc MIXED in SAS. In addition to the longitudinal analysis, the model also permits cross-sectional analyses (comparing outcomes by condition), which we will perform at baseline, and at the post intervention follow-up. In addition, to the cross-sectional analyses comparing the main effect of treatment we will also examine main effects for race/ethnicity and treatment by race interactions. We have specified primary outcome variables for both the caregiver (e.g., CESD) and patient (e.g., HVLT-R). However, as the intervention targets a number of different areas related to patient and caregiver outcomes there are a number of secondary measures. When possible, we will examine and employ a multivariate approach. Using a set of measures that are included in our outcome battery, Schulz et al (2009) created a multivariate outcome and we will employ a similar approach. For the cognitive variables, composite measures will be created using principal axis factoring approaches or selecting measures that load most highly on derived factors representative of a particular domain (e.g., memory).

For each hypothesis, we will consider models that incorporate covariates and interactions in order to examine the effects of potential mediator and moderator variables on outcomes. For example, a potential mediator of caregiver outcomes is improvement in both cognitive and functional status of the patient, which will be incorporated in longitudinal models of change. Similarly, training dosage and adherence to homework assignments captured in real time on the tablet will be examined in relation to outcomes. We are aware that given the relatively modest sample size available for some of the analyses, careful consideration must be given to potential problems such as over parameterization; thus, only a limited number of covariates will be included in each model.

All the study personnel who handle the data completed the CITI course. All the identifying information is removed from the rest of the data as soon as it reaches the Center on Aging and the Center on Aging and Behavioral Research. Only the study coordinator or designee has access to the password protected identifying information of the participant. The signed informed consent forms are stored in a separate double locked room. E-mail encryption is

required when emailing any sensitive data. During transmission of large data files, we will use Weill Cornell's secure file transfer.

8) **Risks to Subjects***

The main objective of the study is to develop and test the efficacy and feasibility of an integrated, dyadic-based intervention program (Caregiving Condition), delivered through technology that will include cognitive/ functional training for the AD patient and engage the caregiver (CG) as a therapy extender. The participants will be answering a series questions and working with an interventionist in learning skills in helping them in coping with their caregiver demands and taking care of themselves.

This intervention is a psycho-behavioral based program and the material that are derived from successful caregiving studies. Participants will not be exposed to any kind of risk. Based on our previous experience, participants might feel tired and experience boredom while completing the assessments. They are not exposed to any other risk while participating in this study.

We believe this is a not greater than minimal risk study.

9) **Potential Benefits to Subjects***

Participants can practice the skills learned in the study in their caregiving activities. Their participation in the study can help investigators in refining future technology-based caregiving intervention program(s) to help diverse caregivers of individuals with Alzheimer's disease or memory problems.

10) **Vulnerable Populations***

The study involves Normal, healthy volunteers who are capable of providing consent to participate in the study.

The research team will not use undue influence or manipulation in order to recruit study participants. Our team has extensive experience in recruiting this population and is aware of the ethical conduct necessary to protect human subjects in research. There are regular meeting to monitor recruitment activities to discuss and review our recruitment practices and efforts. During recruitment activities and presentations in community events, the research team provides and explains the content of the flyer to potential participants, and answers and clarifies any questions/ concerns that potential participant may have. Interested participants are instructed and directed to call the phone number or send an email to the address display in the flyer.

11) **Setting**

The study takes place at the University of Miami Miller School of Medicine Center on Aging and the Weill Cornell Medicine Center on Aging and Behavioral Research and in the participants' homes. The intervention is technology-based, thus facilitating the communication and interaction between RAs and participants. Only study assessments (baseline, 6th month, and 12th month) and select sessions may take place at the participant's home.

In cases where a participant is unable to complete a follow-up assessment in-person, a subset of the assessments will be done by phone in order to obtain outcome measures at the proper timepoint.

12) Resources Available

All the study personnel have their CITI certificate. The PI holds regular meetings with the study coordinator and data manager to review the progress of the study. At the same time, there are weekly meetings on data management and recruitment of participants. There is also a weekly clinical team meeting of assessors who are working one-on-one with the participants to monitor and review the progress of the participants.

The Center on Aging and the Weill Cornell Medicine Center on Aging and Behavioral Research lead by [name] has extensive experience conducting research studies. Most of the members of this study are involved in other on-going studies at the Center. The Center has a computer dedicated to store and process the data. It also has secure room and cabinets to store study-related documentation. In addition, the study team contains assessors who are fully bilingual. They are fluent in both English and Spanish, thus capable of implementing the study in either language.

13) Prior Approvals

NA

14) Recruitment Methods

After IRB approval the research team will contact potential recruitment sites and inform them about the study. These sites will be provided with IRB approved promotional materials (flyer) for recruitment. At the same time, the WCM PR department will be informed and notified of the ongoing research. The PR department will be provided with the promotional materials for the study. WCM sites such as those that make regular postings and newsletters will also be contacted and provided with an approved ad or communication regarding the project. The CITI certified staff members within the project plan to also attend health fairs and /or senior centers and events and have flyers available at various community centers so that potential participants can learn of the study. The WCM approved ad will also be posted in non-WCM newsletters and advertisement sections. Promotional material used in this study are: flyer, radio ad and advertisement blurb.

IRB-approved letters may be sent to designated patients from WCM/NYPH clinics with IRB approval.

Once potential participants learn of the study, they will phone the recruitment phone line. A brief telephone interview will be conducted. If these participants are eligible for the study, they will then be scheduled for the baseline assessment.

Participants will not have any financial liabilities for participating in the study. The study provides financial compensation for their time/effort in completing the assessment. Eligible caregiver participants will receive \$30 for each completed assessment, for a total of \$90 (\$30 at baseline, 6-month, 12-month visits). Eligible care recipient participants will receive \$20 for each completed assessment, for a total of \$60 (\$20 at baseline, 6-month and 12-month visits). \$10 will be provided to those that do not meet eligibility.

15) Local Number of Subjects

We anticipate to screen a maximum of 350 participants. We expect 240 participants (120 dyads) to complete the study. 80 participants will be from University of Miami and 160 will be from the Weill Cornell Medicine Center on Aging and Behavioral Research.

16) Confidentiality

This study does not collect specimens. The data are questionnaire based and participants will be completing them on paper or online using a secure and unique log. All the data will be stored and secured using the procedure implemented by the Data Manager of Center on Aging and the Weill Cornell Medicine Center on Aging and Behavioral Research. The access to records and participants data will be allowed only to the study personnel. The data will not contain any identifying information.

The hard copy data will be stored in a double locked office at the Center on Aging and the Weill Cornell Medicine Center on Aging and Behavioral Research in the Mental Health building. The electronic and audio recorded data/interview will be kept in server computer at the Center on Aging and the Weill Cornell Medicine Center on Aging and Behavioral Research as well. The data will be backed-up on a regular basis by the Data Manager and the copies will be kept in a double locked office at the Center on Aging and the Weill Cornell Medicine Center on Aging and Behavioral Research. Only study-related staff (listed in the IRB protocol) will have access to the data.

The online data will be collected on REDCap (WCM has approved this survey/data collection service and has a subscription to it). Connections to the server are encrypted. Minimum levels of password complexity will be enforced. The Tablet will be locked down, requiring a 4-digit PIN.

17) Provisions to Protect the Privacy Interests of Subjects

During the informed consent process, participants are made aware of who will have access to the study data (see section of Confidentiality). The participants are instructed to sign the Informed Consent Form only when he/she is completely satisfied with the information in the ICF, and all his/her questions are answered fully. We will not release participant information to anybody who is not listed in the Confidentiality section of the ICF.

18) Consent Process

The research team will not use undue influence or manipulation in order to recruit study participants. Our team has extensive experience in recruiting this population and is aware of the ethical conduct necessary to protect human subjects in research. They are all CITI certified. There are regular meetings to monitor recruitment activities to discuss and review our recruitment practices and efforts. Most of the members of the research team who have an active role in the conduct of the study (screening, assessment, and conducting the study) will also be involved in the recruitment and consent process.

During recruitment activities and presentations in community events, the research team provides and explains the content of the flyer to potential participants, and answers and clarifies any questions/ concerns that potential participant may have. Interested participants are instructed and directed to call the phone number or send an email to the address displayed in the flyer.

The study involves adults who have the capacity to consent. These potential participants are able to read and comprehend the information written in the Informed Consent Form and HIPAA authorization. Questions will be answered and addressed accordingly. Therefore no additional process will be used to obtain consent from them. Care Recipients are required to successfully respond to the Informed Consent Feedback Tool in order to be eligible for participation in the research study.

When a person (caregiver), who is interested in the study contacts us via telephone or email to request information, a trained and certified screener/assessor will call the participant back and explain the basics of the study. Then they will ask the participant's permission to proceed with the telephone screening questionnaire that would lead us to make a decision as to whether or not he or she might be an appropriate candidate for the study or basically would qualify for the study. This process is a preliminary screening done over the telephone, which is not feasible to do by having a written consent. If and only when a person 1) has agreed to be screened over the phone; 2) understands that this study represents research; and 3) understands their participation is voluntary and that they can withdraw their consent at any time, will the screening process proceed. We will not obtain a written consent form for the phone screening process as this research presents no more than minimal risk of harm to subjects and involves no procedures for which written consent is normally required outside of the research context (45 CFR 46.117 (c) (2). It is not possible to have written consent from each potential participant for practical as well as cost reasons.

Upon the completion of the telephone screening and if the participant appears eligible for the study, a home or virtual visit by one of the research team members (CITI certified) will be scheduled. A written informed consent form will be obtained by the CITI-certified and protocol trained RA during the first visit. Before any additional study-specific information is obtained, participants will be asked to read the IRB-approved consent form. The potential participant is asked to read the consent form and, if agreeable to participate, sign it in the presence of an assessor. If consenting virtually, the participant will follow the IRB-approved method.

During the phone screening process and other screening steps and after the potential participant verbally consents to participating in the study, they will be scheduled for an appointment for a baseline assessment.

19) Process to Document Consent in Writing

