Protocol

Title: A Non-pharmacological Intervention for Patients With Alzheimer's Disease and Family Caregivers (Care Partners Program)

NCT#: NCT03333252

Date: December 10, 2020

1) Protocol Title

Care Partners Program – CP Program

2) Objectives*

This study protocol describes the study that is sponsored by Florida Department of Health and by the National Institutes of Health/National Institute on Aging. Both entities provide support for the design, conduct, and data analysis of the study.

This study will evaluate the efficacy and feasibility of an innovative dyadic non-pharmacological intervention (DT) that is delivered through an interactive state-of-the-art technology that includes an evidenced-based **caregiver component** modeled after REACH II (Belle et al., 2006) **augmented** by an evidenced-based cognitive and functional training component for the **individual with AD (care recipient)** (Acevedo & [name], 2007; [name] et al., 2004, 2006). The program is designed to: be synergistic; emphasize issues important to caregivers in the earlier stages of caregiving; help the caregiver prepare for caregiving transitions; and engage the caregiver as a therapy extender. The program will be tailored for the CG using a risk appraisal approach (Czaja et. al., 2009) and for the CR. It will also be culturally tailored and based on a community-based and stage-model approach to intervention development. The DT intervention will be compared to a control condition (CC) that includes non-specific mental stimulation for the CR and a nutrition intervention for the CG (we chose this for equivalent contact time). Two hundred and forty dyads will be randomly assigned to the DT or CC conditions. The proposed DT intervention builds on: the findings of our group that specific cognitive training techniques can result in improvement and maintenance of gains in cognitive and functional performance in mild stage AD patients (e.g., Acevedo & [name], 2007); our evidenced caregiver interventions (e.g., Belle et al., 2006); our technology-based interventions (e.g. Eisdorfer, Czaja et al., 2003; Czaja et al., 2013) and our on-going technology-based caregiver intervention program (Caring for the Caregiver Network). **The specific aims** of this project are to:

1) Evaluate the efficacy of the DT intervention on CG outcomes.

Hypothesis 1.1: CGs assigned to the DT condition will demonstrate decreased distress and burden relative to CGs assigned to the CC condition.

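### Section 5 gives 240 participants both as the number randomised and as the number expected to complete, so it allows for no loss over 12 months; Sections 2 and 15 also disagree on whether 240 counts dyads or individuals

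*Combined protocol and SAP*

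**What the plan says.** Section 5 (Procedures Involved) gives three counts in consecutive paragraphs:

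- Screening: "We anticipate to screen a maximum of 350 caregiver participants".
- Completion: "We expect 240 participants (caregiver and care recipient) to complete the study".
- Randomisation: "following a baseline assessment, 240 participants will be enrolled and randomly assigned to one of two groups".

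Two other sections use the same number. Section 2 (Objectives) says "Two hundred and forty dyads will be randomly assigned to the DT or CC conditions". Section 15 (Local Number of Subjects) says "We expect 240 participants (120 dyads) to complete the study" and divides that total by site: "80 participants will be from University of Miami and 160 will be from the Weill Cornell Medicine Center".

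Follow-up visits fall at 6 and 12 months, the later one being "one 12-months post session 1 (regardless of when the 6-month visit occurs"). On leaving the study, Section 5 notes, while explaining consent to recording, "Since participants can withdraw their consent anytime during the study". The dyad exclusions in Section 4 remove terminal illness with survival expected to be no more than 6 months, and a nursing home move planned in the next 4 months. No section states an expected rate of loss.

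**The concern.** A number randomised and a number completing 12 months later should differ by an expected loss. Here they are equal, in a population of people with Alzheimer's disease and their caregivers, over a follow-up longer than either exclusion window. The completer figure therefore appears to be the enrolment figure repeated, not a forecast.

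The shifting unit adds to this. A reader cannot tell whether the trial randomises 240 dyads, or 240 individuals in 120 dyads. Nor can a reader tell whether the plan expects to lose nobody or half the dyads. The documents give no power calculation, so these counts are the only statement of the trial's size. If they are wrong or ambiguous, nobody can judge how much 12-month information the comparison will have, or later say whether retention met the plan.

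**Working it through.** **Inputs.** Randomised: 240 participants (Section 5) or 240 dyads (Section 2). Completing: 240 participants (Section 5), or 240 participants in 120 dyads (Section 15). Last assessment: 12 months after session 1 (Section 5). Exclusion windows: 4 and 6 months (Section 4). Attrition rate: none given, so the rates below are assumptions.

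**Step 1: the plan's own figures.** The site split adds up: 80 + 160 = 240. So does Section 15's conversion: 240 / 2 = 120 dyads. No sample-size formula can be reproduced, because the documents give no effect size, standard deviation, power, test-level alpha, allocation ratio or dropout rate. The only alpha given, 0.25, is for screening potential confounders (Section 7).

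**Step 2: implied retention = completers / randomised.**

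| Figures compared | Calculation | Implied retention |
|---|---|---|
| Section 5 randomised and Section 5 completing, one unit | 240 / 240 | 100% |
| Section 2 randomised (240 dyads = 480 people) and Section 15 completing (240 people) | 240 / 480 | 50% |

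Neither value is stated or defended as an assumption.

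**Step 3: is zero loss credible?** If each dyad is lost independently with probability d, the chance that none of n dyads is lost is (1 − d)^n. At an assumed d of only 5%:

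- 240 dyads: 0.95^240 = 0.0000045
- 120 dyads: 0.95^120 = 0.002

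The exclusions do not remove the risk. They leave 12 − 4 = 8 months of follow-up beyond the placement window and 12 − 6 = 6 months beyond the terminal-illness window.

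**Step 4: completers under assumed loss = n × (1 − d).**

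| Assumed 12-month loss | Completing dyads if 240 randomised | Completing dyads if 120 randomised |
|---|---|---|
| 10% | 240 × 0.90 = 216 | 120 × 0.90 = 108 |
| 20% | 240 × 0.80 = 192 | 120 × 0.80 = 96 |
| 30% | 240 × 0.70 = 168 | 120 × 0.70 = 84 |

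Relative to these, a completer figure equal to the number randomised is too high by 11% (240/216), 25% (240/192) or 43% (240/168). The percentages are the same for 120 dyads.

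**The case against.** **The two 240s may not share a unit.** Section 5 qualifies the completers as caregiver and care recipient, leaves the randomised participants unqualified, and counts screening in caregivers. One could read it as 240 dyads randomised and 240 individuals completing. This stands: the zero-loss finding applies only when both figures are in one unit. It does not rescue the text, because the alternative reading implies that half the dyads are lost, which the plan does not state either.

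**The analysis does not need 240 completers.** Section 7 plans a mixed model suited to unbalanced and missing data, and Section 11 with Appendix A offers a reduced telephone assessment when a follow-up cannot be done in person. This stands too. The defect is in the stated size, not in the model. With no power inputs, no loss of power can be computed.

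**The documents permit loss without predicting it.** The withdrawal clause states a right, in a passage about recording, and the exclusion windows show only that loss is possible. That is fair, but possible loss over 12 months is enough to make an expectation of none unrealistic.

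**Stronger readings that the documents do not support.** A reader might infer that 240 completers can be reached only by replacing randomised dyads that leave, so that the comparison drifts towards completers. No section mentions replacement or a completer quota, and the figure is worded as a forecast, which may simply be missed. A reader might also infer that the screening limit of 350 would be nearly used up. That depends on the unit: at an assumed 20% loss, 240 completing dyads need 240 / 0.80 = 300 randomised, or 86% of 350, whereas 120 need 120 / 0.80 = 150, or 43%. Section 15 also counts the 350 as participants, where Section 5 counts caregivers. No conclusion about the limit follows.

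**Conclusion.** The point holds as a defect in the stated numbers. Read in one unit, Section 5 expects 0% loss over 12 months, which is not credible given free withdrawal and exclusion windows of 4 and 6 months. Read across Sections 2 and 15, the same plan implies 50% retention. Both cannot be meant, and neither is presented as an assumption.

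Its size depends on two things that the documents do not settle: the unit and the attrition rate. Over an assumed 10% to 30% loss, expected completers are 216 to 168 dyads if 240 are randomised, or 108 to 84 if 120 are. The finding does not extend to bias in the treatment comparison, to a replacement procedure or to a measured loss of power. It should be corrected because these counts are the plan's only statement of size and the correction is cheap.

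**What to change.** 1. In Sections 2, 5 and 15, state the number to be randomised once, in dyads. The sponsor must confirm whether it is 240 or 120. Give individuals only as twice that number, and put the site split and the screening figure in a stated unit.
2. Describe that number as the randomisation target.
3. Add an explicit attrition assumption, with its source, and restate expected completing dyads at 6 and 12 months below the number randomised. Step 4 of the working shows the 12-month figures for a range of assumed rates; the rate itself is for the sponsor to justify.
4. In Section 7, state that all randomised dyads stay in the mixed-model analysis, whether or not they complete.

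This is protocol wording. It proposes no extra enrolment, visits or data collection. The only downside is that the stated number of completers becomes less favourable.
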